1.0 Objectives and Specific Aims

Goal: *To evaluate the impact of increased frequency and intensity of Physical Therapy (PT) services on patient outcomes in the acute stroke population.*

Aim I: To determine whether increasing the frequency of Physical Therapy services post-acute stroke is superior to standard of care physical therapy services; measured by a change in functional outcomes, hospital length of stay, 30 day follow up.

Hypothesis I: We hypothesize that patients receiving an increased frequency of PT services will demonstrate higher degree of improvement on the Activity Measure for Post-Acute Care (AMPAC) and Postural Assessment Stroke Scale (PASS) from admission to time of discharge from the hospital and at 30-day follow up. We also expect lower overall Modified Rankin Scale (mRS) scores for the increased frequency PT group compared the usual care PT group at 30 days post stroke.

Aim II: To determine whether increasing the intensity of Physical Therapy services post-acute stroke is superior to standard of care physical therapy services; measured by a change in functional outcomes, hospital length of stay, 30 day follow up.

Hypothesis II: We hypothesize that patients receiving an increased intensity of PT services will demonstrate higher degree of improvement on the AMPAC and PASS from admission to time of discharge from the hospital and at 30-day follow up. We also expect lower overall mRS scores for the increased frequency PT group compared the usual care PT group at 30 days post stroke.

Aim III: To determine whether increasing the intensity of Physical Therapy (PT) services post-acute stroke is superior to increasing the frequency of PT services; measured by a change in functional outcomes, hospital length of stay, 30 day follow up.

Hypothesis III: We hypothesize that patients receiving an increased intensity of PT services will demonstrate higher degree of improvement on the AMPAC and PASS from admission to time of discharge from the hospital and at 30-day follow up. We also expect lower overall mRS scores for the increased intensity PT group compared the increased frequency PT group at 30 days post stroke.

Aim IV: To determine whether increasing the intensity and frequency of PT services post-acute stroke is superior to increasing only the intensity of PT services; measured by a change in functional outcomes, hospital length of stay, 30 day follow up.

Hypothesis IV: We hypothesize that patients receiving an increased frequency AND intensity of PT services will demonstrate higher degree of improvement on the Activity Measure for Post-Acute Care (AMPAC) and Postural Assessment Stroke Scale (PASS) from admission to time of discharge from the hospital and at 30-day follow up. We also expect lower overall Modified Rankin Scale (mRS) scores for the combined increased intensity AND frequency PT group compared the usual care PT group OR either of the treatment groups alone at three months post stroke.

2.0 Background

The Department of Physical Therapy in conjunction with the Comprehensive Stroke Center at the Medical University of South Carolina (MUSC) seeks support for developing an evidence-based approach for the mobilization of patients within the first 24 hours of admission for an acute stroke and for increasing the frequency and intensity of acute PT services while inpatient. This evidence will prepare physical therapists and guide practice in the delivery of acute stroke mobilization in the hospital setting to optimize length of stay, disposition planning, and enhance long term recovery outcomes.

Our research hopes to challenge the clinical paradigm regarding the possibility of decreased functional outcomes with early mobilization post stroke. We acknowledge that acute stroke patients may not be able to tolerate an extensive early mobility program but may benefit from shorter more frequent sessions of therapy early in their recovery. Throughout the literature, there are clinical practice guidelines for both the inpatient rehabilitation and outpatient therapy sectors and post stroke recovery. Little is known about the contribution of therapy services in the acute hospital setting and therapy's impact on long term functional gains. The goal of this project is to determine the appropriate dosage of post stroke mobility in the acute care hospital setting.

The objective is to determine if changing one component of the overall mobility dosage, adjusting frequency or intensity, will improve patient outcomes. Phase I of this study, performed at MUSC from June 2021-June 2022, demonstrated improved functional mobility outcomes at hospital discharge for patients who received a combination of both increased frequency and intensity of PT services compared to the standard of care approach. Phase II aims to determine if these promising results can be attributed to increased frequency, increased intensity or a combination of frequent and intense PT sessions. As a comprehensive stroke center, MUSC strives to provide the best of patient care by committing to a higher standard of clinical service utilizing evidence-based practice to improve patient outcomes.

3.0 Innovation of Intervention to be Studied

Early mobilization is a widely accepted pillar of acute hospital physical therapy services. In most populations, early mobility is regarded as safe, feasible, and yields positive results.⁶ A considerable amount of clinical and scientific literature has evaluated and upheld the positive effect of early mobility on patient safety, ICU delirium, duration of mechanical ventilation, hospital length of stay, functional mobility, ambulation ability, and mortality. However, most of the research in the field of early mobilization has focused on intensive care patients with multiple medical comorbidities.⁷

The consideration of an acute stroke diagnosis in relation to the approach of acute care PT and "early mobility" is limited. The AVERT trial was novel in opening the doors to evaluate physical therapy's approach to acute stroke care on dedicated stroke units. This research proved critical since earlier research surmised that complications of immobility could be estimated to account for as many as 51% of death in the first 30 days post stroke.⁸ The results of the AVERT trial raised concern that very early mobilization may cause changes in cerebral blood flow and blood pressure leading to worsened stroke outcomes, increased mortality and increased rate of falls during early mobility.⁹

From the publication of the AVERT trial, there has been a rise in clinical interest regarding the correlation of early mobility and improved functional outcomes post stroke with the biggest question remaining- how early is too early and how much is too much? The majority of physical therapy studies in the acute stroke population have only examined the optimal time to begin mobilization post admission to the hospital.⁹ We hypothesize that the approach of shorter, more frequent sessions of intense quality therapy services will negate the post stroke cerebral perfusion factor. Thus, allowing patients to progress functional mobility with improved tolerance to therapy sessions, frequent repetition, as well as implementation of motor learning principles to ensure carryover by providing distributed over massed practice.

The research in the field of neuroplasticity and neuro rehabilitation illustrates the importance of high intensity, repetitive and aggressive approaches for motor recovery, however, most of this research has been performed in the subacute stroke population. Error augmentation training is one way to increase the difficulty of a task to enhance motor learning.¹⁰ In the current research, error amplification training was found to induce more robust aftereffects of locomotion training as compared to assistive training.¹⁰ Thus, error augmentation/ amplification may be one approach to increasing the intensity and complexity of the task without changing the task itself. For acute stroke patients in the hospital setting- error augmentation can be implemented by targeting the patients post stroke deficits by emphasizing them. If a patient has a hemiparetic limb- error augmentation would include resisting and challenging the movement of that limb rather than facilitating and assisting with the movement of that limb. For patients whose stroke did not cause hemiparesis but rather balance impairments, narrowing the base of support or dynamically resisting balance in the direction of a patient's lateral lean can also amplify and augment their error. The celebrated motor learning theory, "The Challenge Point Theory" states that learning is maximized when the task difficulty is appropriate for the individual skill level of the performer¹¹; this theory leaves us with hope that increasing the challenge of mobility tasks in the acute hospital setting may be beneficial to increasing the success and progress of functional mobility.

Rather than decreasing the time to upright mobility, it may be beneficial to examine the effect of short sessions of more frequent challenging mobilization in these patients, within the early stages of their hospitalization. If, as assumed, a prolonged duration of upright sitting posture has a negative effect on cerebral blood flow¹² it may be possible to gain the positive effects of early mobility by continuing to provide PT services while combating the negative effects of cerebral perfusion by returning all patients to a <30-degree position in bed following therapy services within the first 24 hours of acute stroke admission. This study aims to examine the approach of increased frequency and intensity of physical therapy services as a way to gain the benefits of the publicized early mobility approach, while weighing the concerns raised by previous trials and decreasing amount of time left upright to combat negative effects of cerebral perfusion on the ischemic penumbra. A study similar to our Phase I approach, performed in Taiwan in 2021, demonstrated that survivors of acute stroke who receive up to 2 rehabilitation sessions per day for 5 d/wk. early in their hospitalization have better functional recovery at 3 months after stroke.¹³ Phase I of "Impact of Intense Physical Therapy on Functional Mobility Outcomes in the Acute Stroke Population" demonstrated a significant improvement in functional mobility scores for acute stroke patients mobilized early, frequently and intensely compared to their counterparts in the standard of care arm of the study. The treatment arm progressed on the Postural Assessment Scale for Stroke (PASS) and the Activity Measure for Post-Acute Care (AMPAC). The PASS improved in the experimental group from admission to discharge 6.28 points while the standard of care change was 1.82 points; there was a main effect for interaction ($p=0.0001$). The AMPAC improved in the experimental group from admission to discharge 3.13 points while the standard of care change was 1.48 points; there was a main effect for interaction ($p=0.01$). PASS and AMPAC scores were maintained in both groups at 90 days post-stroke. The level of disability measured by the Modified Rankin Score (mRS) decreased for both groups at 90 day follow up and the length of hospital stay was decreased by 1.5 days in the treatment arm. There was one significant adverse event in the experimental group during the first 30 days post-stroke- due to significant atherosclerosis and perfusion dependence. This patient was removed from the study secondary to having a carotid stent placed. Because of this adverse event, patients who

require stenting procedures were added to the list of exclusion criteria for Phase II. Given the feedback on AVERT results assuming that most negative outcomes were for the patients with hemorrhagic stroke, not ischemic stroke- Phase II of this study will also exclude all hemorrhagic stroke patients. We demonstrated in phase I that patients may benefit from shorter more frequent sessions of therapy early in their recovery with an emphasis on facilitating error to progress seated postural control, motor recruitment strategies, and transfer training delivered in separate sessions- allowing for time outside of therapy to be spent in a less than 30-degree position for the first 24 hours of hospital admission to optimize cerebral perfusion. During phase I, the treatment arm was seen both frequently and intensely. Phase II of this study is hopeful to determine whether the improvements in functional mobility during Phase I should be attributed most to an increase in intensity, an increase in frequency or whether the combination of frequent and intensive therapy is truly best practice for acute post stroke PT services in the hospital setting.

4.0 Approach

The purpose of this study is to determine what amount of physical therapy is beneficial in the hospital setting after suffering a stroke. Stroke continues to be a leading cause of disability and death worldwide. Improvements in research, acute stroke treatments, and health care accessibility have resulted in a decreased mortality rate of stroke patients and have increased the need for rehabilitation services to optimize functional gains post-acute stroke. Across most acute health conditions, increased physical therapy (PT) in the hospital environment has been shown to reduce length of stay and improve quality of life. However, the dose-response relationship is not well established in acute stroke patients. There is conflicting literature regarding the safety of early mobility within the first 24 hours post admission to the hospital for an acute stroke. Phase I of this study was performed at MUSC from June 2021-June 2022 with promising results of improved functional mobility outcomes with early intervention of Physical Therapy post stroke. Phase II aims to evaluate whether the dosage of increased frequency or increased intensity of Physical Therapy services led to the promising outcomes and functional improvements which the first study demonstrated.

We propose to enroll 168 individuals with acute stroke admitted to MUSC and randomize them into increased frequency, increased intensity, increased frequency and intensity combined and usual care PT treatment groups. This study will be designed as a randomized control trial. Patients who agree to participate, will be assigned (at random) to either a treatment arm which will receive either more frequent therapy services, more intense therapy services (increased intensity by incorporating error augmentation training), a combination of frequent and intense therapy services (frequent bouts of error augmentation training) or to the control group (treatment as usual) which will receive the standard amount of therapy services currently provided in the hospital setting (~3-5 times per week). Error augmentation training is an approach that targets what is difficult for the patient and makes it even more difficult, increasing errors to enhance adaptation. By studying the balance, walking and success of patients in the treatment groups compared with the standard of care group- we hope to better understand the contribution of intense PT services, frequency PT services, or a combination of intense and frequent PT services on a patient's independence post stroke. We know from phase I of this study that patients provided with a combination of increased frequency and intensity of PT services demonstrated significant functional improvements (measured by PASS and AMPAC) at

time of hospital discharge and a decreased length of hospital stay when compared to the standard of care PT group. Phase II will help us determine if these promising results can be best attributed to the intensity and error augmentation training portion of PT services, to the frequency of PT services, or to a combination of both frequent and intense PT services post stroke in the acute hospital setting.

5.0 Study Endpoints

Physical Performance and Functional Measures: PASS scores & AMPAC scores on evaluation, day three, discharge, and 30-day follow up. Discharge disposition recommended vs ultimate discharge disposition, hospital length of stay, and 30-day readmission. The primary outcome is a change in functional mobility measure- the Postural Assessment Scale for Stroke from PT evaluation to discharge from hospital.

6.0 Setting

This research will be conducted on the inpatient stroke service at MUSC (ED, 9E, 9W, 8W, ICU) as soon as possible after admission, ideally within the first 24 hours of the patient's admission to the vascular neurology service for an acute stroke. Follow up values will be collected at post discharge neurology clinic (either in person or through password protected zoom call, or doxy.me) by a member of the study team. Adverse events will be documented in the patient's medical chart and research record and the primary investigator will direct and oversee services provided.

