If a patient is randomized to the frequent AND intense physical therapy treatment group they will receive PT services 2x/day for 3 out of the first 5 days of hospital admission and daily for the remainder of the hospitalization. Sessions will be 20-50 minutes in duration (based on patient tolerance) and will focus on increasing the intensity of services by making difficult tasks more difficult with the addition of resistance or other challenges. This is known as “Error Augmentation training” and will be implemented to target at least 3 post stroke deficits identified on evaluation. If a patient is randomized to the standard of care group they will receive the normal amount of PT services one a day, three to five days week for 20-50minutes throughout admission. The patient will be assisted to perform transfers and mobility tasks with a PT providing facilitation to assist the patient without the component of an added challenge.

Functional measures such as PASS, AMPAC, mRS will be collected on initial PT evaluation, day three of treatment and discharge from the acute care hospital. These measures will be collected again in the outpatient neurology clinic (or virtually via Zoom or Doxy.me) at 30 day follow up appointment. Study procedures will end after 30 day follow up appointment is completed.

Participants can ask to end PT sessions early if they become uncomfortable or do not want to do them.

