12.0 Outcomes and Analysis

Goal enrollment is 168 participants. Based on the past literature, in similar populations the standard deviation of PASS measurements is at the most 7.20.⁵ Using this, with a sample of 42 patients in each group, with 95% confidence at the end of the study we can estimate this difference within a margin of error of 2.8.

The primary outcome measure will be the change in postural assessment stroke scale scores from time of PT evaluation to hospital discharge. A factorial design will allow for a test of intensity (vs control) and duration (vs control) through pooling across treatment arms. Using the table below, margins (A+C, B+D, A+B, C+D) need to each be 104 given a mean difference of 2.8, standard deviation of 7.2, 80% power and 5% type I error. Given that this is an early phase study, we can increase the type I error to 10% which would decrease the overall sample size needed to 168 patients (42 per arm) whilst still maintaining 80% power.

	Low Intensity	High Intensity	Totals
Low Duration	A	B	A+B
High Duration	C	D	C+D
Totals	A+C	B+D	A+B+C+D

We are planning to conduct the analysis using intention to treat paradigm. In a preliminary analysis we will compute all summary statistics. Initial plots, such as spaghetti plots, will be used to guide our analyses. A general linear mixed model approach will be used to analyze all the outcomes. This model will account for the correlations between time points using either a compound symmetric or spatial structure for the covariance matrix. Post-hoc analyses using Tukey type adjustments will be performed to obtain least squares estimates of the differences between the two randomized groups. Although the study is powered based on only the primary

outcome (PASS), we will apply multiple comparisons adjustments for the rest of the outcomes, using Bonferroni corrections. We will test for the assumptions using diagnostic procedures and take appropriate actions if needed. Also, we will define an outcome to be ‘favorable’ or ‘unfavorable’ based on a threshold and apply generalized linear mixed models with logistic link and repeat the analyses. We will attempt to minimize drop-outs but in case of missing data, we will assume Missing at Random or Missing Completely at Random. If necessary, we will perform multiple imputations. For all analyses, we will use SAS, (MIXED, GLIMMIX, MI and MIANALYZE).

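### The 30-day mRS has no collection route besides a clinic visit or video call, so its loss may depend on disability; a telephone fallback is a cheap remedy for this secondary measure

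*Combined protocol and SAP*

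**What the plan says.** Section 6.0 (Setting) fixes where follow-up data come from: "Follow up values will be collected at post discharge neurology clinic (either in person or through password protected zoom call, or doxy.me". A member of the study team does the collecting.

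Section 9.0 (Study Design) names the measures, "Functional measures such as PASS, AMPAC, mRS will be collected on initial PT evaluation", adds day three and discharge, and then says of the last time point: "These measures will be collected again in the outpatient neurology clinic (or virtually via Zoom or Doxy.me) at 30 day follow up appointment". Study procedures end with that appointment. No section provides for an ordinary telephone call, a caregiver or facility report, or an assessment during a readmission.

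Section 1.0 uses the 30-day mRS in three hypotheses. Hypotheses I and II share the phrase "for the increased frequency PT group compared the usual care PT group at 30 days post stroke" (Hypothesis II names the frequency group although its aim concerns intensity). Hypothesis III reads "for the increased intensity PT group compared the increased frequency PT group at 30 days post stroke". Hypothesis IV differs: "compared the usual care PT group OR either of the treatment groups alone at three months post stroke".

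Section 5.0 makes PASS change from evaluation to discharge the primary outcome. It lists 30-day readmission and discharge disposition among the endpoints and does not list mRS.

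Section 12.0 plans a general linear mixed model for all outcomes and, "in case of missing data, we will assume Missing at Random or Missing Completely at Random", with multiple imputation if necessary. It plans no analysis under other missingness assumptions. The sample size carries no stated allowance for loss.

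**The concern.** Keeping a 30-day appointment is a post-randomisation event, and it plausibly depends on the function that mRS grades. Entry allows NIHSS up to 18 with motor involvement (Section 7.0), therapy includes wheelchair use for patients unable to walk (Section 9.0), and readmission is an endpoint. The plan therefore expects some patients for whom a clinic visit or a video appointment may be difficult. If they are missed, the observed 30-day mRS describes a fitter group than was randomised.

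A mixed model or imputation that uses the evaluation, day-three and discharge scores handles the part of this loss that those scores predict. It does not handle loss driven by what happens after discharge, such as failure to recover or a readmission, unless observed data explain it. At stake are precision and some dilution of the mRS comparisons in Hypotheses I to III. A score not obtained at 30 days may not be recoverable later, so the route has to be in place beforehand.

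**Working it through.** **The plan's own figure.** Section 12.0 sizes the trial on PASS only: difference 2.8, SD 7.2, 80% power. With n per margin = 2(z₁₋α/₂ + z₀.₈₀)² × SD² / difference²:

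- two-sided 5%: 2 × (1.960 + 0.842)² × 51.84 / 7.84 ≈ 103.8, so 104, as stated;
- two-sided 10%: 2 × (1.645 + 0.842)² × 51.84 / 7.84 ≈ 81.8, so 82 per margin and 164 in total, close to the stated 168.

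The documents give no corresponding figure for mRS, its distribution or its completeness. Everything below rests on assumptions chosen to show a range.

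**Assumed inputs.**

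- True mRS at 30 days, grades 0 to 5. Control: .10/.20/.20/.20/.20/.10, mean 2.50. Treated: .15/.25/.20/.18/.15/.07, mean 2.14. True difference: 0.36.
- Attendance by grade, the same in both arms. Mild: 95% for grades 0–2, 85% for 3, 70% for 4–5. Heavier: 95% for 0–1, 90% for 2, 65% for 3, 40% for 4–5.

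**Values lost.** Proportion observed = Σ p(grade) × attendance(grade).

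- Mild, control: .50 × .95 + .20 × .85 + .30 × .70 = .855, so 14.5% lost. Treated: .60 × .95 + .18 × .85 + .22 × .70 = .877, so 12.3% lost.
- Heavier, control: .30 × .95 + .20 × .90 + .20 × .65 + .30 × .40 = .715, so 28.5% lost. Treated: .40 × .95 + .20 × .90 + .18 × .65 + .22 × .40 = .765, so 23.5% lost.

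In an arm of 42, that is about 5 (42 × .123) to 12 (42 × .285) patients.

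**Complete-case difference.** Observed mean = Σ grade × p × attendance / proportion observed.

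| Scenario | Control mean | Treated mean | Difference | Shrinkage |
|---|---|---|---|---|
| No loss | 2.50 | 2.14 | 0.360 | – |
| Mild | 1.990/.855 = 2.33 | 1.742/.877 = 1.99 | 0.342 | 5% |
| Heavier | 1.460/.715 = 2.04 | 1.329/.765 = 1.74 | 0.305 | 15% |

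Missing control patients average (2.50 − 1.990)/.145 = 3.5 in the mild scenario and (2.50 − 1.460)/.285 = 3.6 in the heavier one.

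**What earlier scores recover.** With the same attendance patterns, 30-day mRS was imputed linearly from discharge mRS alone, at an assumed latent correlation of 0.5 to 0.85. The difference recovered was about 0.34–0.35 in the mild scenario (2–4% shrinkage) and 0.32–0.35 in the heavier one (roughly 4–12%). Within these scenarios, therefore, the 5–15% is an upper figure.

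**If loss differs by arm.** Assume no true effect, 45% poor outcome in both arms, and 5% loss among good outcomes. The observed poor rate is .45(1 − L) / [.45(1 − L) + .55 × .95]. With L = 10% in one arm and 30% in the other, the rates are 43.7% and 37.6%, a false difference of 6.1 points. By contrast, take true rates of 50% and 40% and equal loss by outcome in both arms (L = 10%, 20% or 40%). The 10-point difference is then observed as 9.9, 9.8 or 9.1 points.

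**The case against.** The best case for the plan has four parts.

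- **Video already helps.** It can reach patients who cannot travel, including some in a facility or readmitted, and nothing bars a caregiver from assisting. Entry requires orientation, command-following and capacity to consent, which narrows the group unable to use video. This stands in part: a video call still needs a device and a kept appointment, and post-discharge events can change who manages either.
- **The planned analysis is not complete-case.** mRS is also taken at evaluation, day three and discharge, and the mixed model uses those scores. This stands, which is why the shrinkage above is not a forecast.
- **mRS is not the primary outcome** and is absent from Section 5.0. This stands and sets the priority.
- **Fallback calls mix modes**, and a visit-only analysis reinstates the selection it is meant to check. This also stands, so visit-only scores can describe mode but cannot validate the result.

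That mRS can be graded by telephone is not stated in the documents. The plan does already accept it by video, so it does not depend on hands-on assessment.

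A reader might infer more than the text supports:

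- *Disabled patients will drop out.* No loss rate is given, so this is a possibility and not a finding.
- *Every hypothesis uses the 30-day mRS.* Hypothesis IV states three months.
- *The comparison will show a false benefit.* Loss that depends on grade equally in all arms dilutes a difference. A spurious one needs loss that differs between arms, and the documents give no ground to expect that.
- *Power falls from 47% to 41% or 35%.* Those figures follow from the assumptions above for complete cases, 84 against 84, at two-sided 10%. Hypotheses I to III are worded arm against arm (42 each) and Section 12.0 applies Bonferroni corrections beyond PASS, so this is not the power of any planned mRS test.

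**Conclusion.** The gap holds on the text. All 30-day values, including the mRS in Hypotheses I to III, depend on a clinic visit or a video call, and nothing else is provided for patients who can do neither. Resulting loss may depend on post-discharge disability, which the missing-at-random assumption covers only as far as observed scores explain it.

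The size is uncertain and probably modest. Under the assumed mRS distributions and attendance, 12–29% of values are lost and the complete-case difference shrinks by 5–15%, less once earlier scores are used. Both figures would change with other distributions, and the bound fails if attendance at a given grade differs by arm. PASS change to discharge is untouched. This is a low-cost improvement to a secondary measure.

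A separate matter: Hypothesis IV places mRS at three months while Section 9.0 ends procedures at 30 days. Those passages must be reconciled, and the present fix does not do that.

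**What to change.** **Sections 6.0 and 9.0.** Add: if the 30-day visit is not held in person or by video, an existing study team member obtains mRS by telephone from the patient, a caregiver or the facility, using a fixed question set, and records the mode and the respondent. Collection of PASS and AMPAC stays as planned.

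**Section 12.0.** State that the 30-day mRS analysis uses scores from all modes. Report the number of missing 30-day mRS values by arm. Show visit-based scores only as a descriptive check on mode, because restricting to them brings back the selection.

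**Cost.** A short call for each patient without a visit, a few protocol sentences, and database fields for mode and respondent. The drawback is mixed collection modes, with telephone or proxy scores likely to be more common among disabled patients. The mode field makes this visible but does not remove it.
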